### **12.3. Data Monitoring Committee**

An independent DMC will review safety data. The DMC will meet on a scheduled basis at least 3 times: once after every 12 enrolled subjects have completed 28 days of dosing through Part 3 of the study. The DMC will also be convened at any time upon meeting the criteria listed in Section 12.2 or at other times as requested. A separate DMC charter, maintained in the trial master file, will describe membership, roles, timing of DMC review, and responsibilities of the DMC members.

### 13. STATISTICS

#### 13.1. Sample Size Considerations

Given that the BCX7353 response rate is unknown, the sample size was kept flexible to cover a range of response options that would achieve 90% power with an alpha of 0.05. The study population is expected to have a mean baseline attack rate of 1 attack/week. The expected mean reduction in attack rate of 350 mg BCX7353 QD is at least 70%. The mean reduction in attack rate in the placebo group may be as high as 30%. Sample size sensitivity assessments provided in [Table 5](#) and [Table 6](#) are based on various BCX7353 and placebo responses and variability.

**Table 5: Power assessment based on sample size and on-study attack rate**

Placebo			BCX7353			Power
Mean	SD	n	Mean	SD	N	
0.7	0.45	12	0.3	0.3	12	68%
0.7	0.45	12	0.3	0.45	12	55%
0.7	0.45	18	0.3	0.3	18	86%
0.7	0.45	18	0.3	0.45	18	74%
0.8	0.45	12	0.3	0.3	12	86%
0.8	0.45	12	0.3	0.4	12	79%
0.8	0.45	12	0.3	0.5	12	69%
0.8	0.45	18	0.3	0.3	18	97%
0.8	0.45	18	0.3	0.4	18	93%
0.8	0.45	18	0.3	0.5	18	87%

Note: Calculations were based on a 2-sided test at significance level of 0.05 and rates and SD are expressed in units.

**Table 6: Power assessment based on sample size and attack free proportion**

Placebo		BCX7353				
N	Attack Free	N	70% Attack Free	75% Attack Free	80% Attack Free	85% Attack Free
12	15%	12	85%	91%	95%	98%
12	20%	12	76%	84%	91%	95%
12	25%	12	67%	76%	84%	91%
18	20%	18	90%	95%	98%	99%
18	25%	18	83%	90%	95%	98%
18	30%	18	73%	83%	90%	95%

Note: Calculations were based on a 2-sided test at significance level of 0.05.

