### **5.3.3. Study BCX7353-203**

Interim efficacy, safety, PK, PD, and PK/PD results are available for Parts 1 and 2 of this ongoing proof-of-concept Phase 2 study in subjects with HAE. As of the cut-off date of 19 May 2017, 51 subjects with HAE were randomized and had received up to 28 days of treatment with BCX7353 once daily; 18 subjects received BCX7353 350 mg, 6 subjects received BCX7353 250 mg, and 7 subjects received BCX7353 125 mg. In addition, 20 subjects with HAE had received placebo. Part 3 of the study is currently ongoing.

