#### **13.2.4. Analysis of Efficacy Variables**

As discussed in Section 7.2.1, each subject-reported HAE attack must be confirmed by an independent adjudication panel prior to inclusion in any statistical analysis or summary of efficacy.

There are no formal hypotheses planned for the study. The primary efficacy endpoint is the number of confirmed HAE attacks in the FAS population. The number of HAE attacks will be analyzed by treatment group using appropriate descriptive statistics as follows: weekly attack rate, counts of attacks, proportion of subjects with no attacks, and number of attack-free days. The relative change in attack rate from placebo will also be calculated for each active arm. Efficacy analyses will be conducted for HAE attacks reported over the entire dosing interval (Days 1 to 28 inclusive) and during the dosing period in which BCX7353 should be at steady-state conditions (Days 8 to 28, inclusive).

Efficacy endpoints will be summarized and listed for each treatment group. Between-treatment comparisons (active vs placebo and between active dose groups) for continuous efficacy variables will be performed using an analysis of variance (ANOVA) and an analysis of covariance (ANCOVA) model. The between treatment comparisons for the proportion of subjects who are attack free will be compared using a Fisher's exact test. A general linear model will be used to test the dose response. Additional statistical models may be considered and details will be provided in the statistical analysis plan.

There will be no adjustments for multiplicity and all statistical tests will be 2-sided with an alpha of 0.05.

Secondary efficacy endpoints including attack severity, location, duration and symptoms of attacks, and number of attacks requiring attack medication will be summarized for each treatment group.

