## **12. EFFICACY ANALYSES**

The efficacy data will be summarized descriptively using the FAS and PP populations. Placebo subjects will be pooled across study parts for the final analyses. An overall summary by treatment group will be provided for each dosing period (i.e., entire and effective) defined in section 10.8 to show:

- Number and percentage of subjects who reported at least 1 attack (non-adjudicated), and total number of subject reported attacks
- Number of and percentage of subjects who reported at least 1 confirmed attack , and total number of confirmed attacks
- Number of and percentage of subjects who reported at least 1 confirmed attack that required treatment, and total number and percentage of confirmed attacks that required treatment
- Number of and percentage of subjects who reported at least 1 confirmed attack that did not require treatment, and total number and percentage of confirmed attacks that did not require treatment

Inferential comparisons of the efficacy endpoints will be performed for each BCX7353 dose vs. Placebo and for pairwise dose groups. The FAS and PP populations will be used for the comparisons of efficacy endpoints. All efficacy data collected on CRF will be listed. A separate listing will be provided for the derived efficacy endpoints.

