### **12.1. Statistical Analysis Methods**

#### **12.1.1. Analysis of Primary Efficacy Endpoint**

The primary efficacy endpoint is the number of confirmed HAE attacks in the FAS and PP populations. The number of HAE attacks will be analyzed by treatment group using appropriate descriptive statistics for the weekly attack rate, change and percentage change from baseline in attack rate, proportion of subjects with no attacks, and number of attack-free days. Efficacy analyses will be conducted for HAE attacks reported over the entire dosing interval (Days 1 to 28 inclusive) and during the effective dosing period in which BCX7353 should be at steady-state conditions (Days 8 to 28, inclusive). Efficacy endpoints will be summarized and listed for each treatment group.

Between-treatment comparisons (active vs. placebo and between active dose groups) for the weekly attack rate will be performed using an analysis of variance model and an analysis of covariance (ANCOVA) model. The adjusted qualifying attack rate will be included as a covariate in the ANCOVA model. The LSM for each treatment arm and the relative difference and associated 95% confidence intervals in attack rate between placebo and each active arm will also be calculated. If the difference between the 350mg and placebo is statistically significant,

additional dose response assessments will be analyzed based on the Tukey, Ciminera, and Heyse trend test.

The between treatment comparisons for the proportion of subjects who are attack free will be compared using a Fisher's exact test. If data warrant, a general linear model (Logistic regression) will also be used to test the dose response.

There will be no adjustments for multiplicity or previous interim analyses, if conducted, and all statistical tests will be 2-sided with an alpha of 0.05.

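### The attack-free power table (Protocol Table 6, SAP Table 3) does not give the power of the planned two-sided Fisher's exact test; Fisher power is 0.6 to 17.3 points lower, and 8 of the 15 cells stated at 90% or more fall below 90%

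*Protocol*

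**What the plan says.** Protocol 13.1 (the same text is in SAP Section 5) says that "the sample size was kept flexible to cover a range of response options that would achieve 90% power with an alpha of 0.05", and offers Tables 5 and 6 as sensitivity assessments. Table 6, identical to SAP Table 3, covers the proportion of subjects who are attack free. It has 12 or 18 subjects per arm, placebo attack-free proportions of 15% to 30%, and BCX7353 proportions of 70% to 85%. The only description of the method is the note: "Calculations were based on a 2-sided test at significance level of 0.05".

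The analysis is described elsewhere. SAP 12.1.1 states: "The between treatment comparisons for the proportion of subjects who are attack free will be compared using a Fisher's exact test". The Protocol says the same in the Synopsis and in 13.2.4. On sidedness and level, 13.2.4 adds: "There will be no adjustments for multiplicity and all statistical tests will be 2-sided with an alpha of 0.05". SAP Section 12 states: "Placebo subjects will be pooled across study parts for the final analyses".

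**The concern.** A power table is informative only if it describes the test that will be run. Fisher's exact test is conservative in small samples, so at 12 or 18 per arm its power can be far below that of an uncorrected chi-square test. If Table 6 was built on a less conservative test, the range of response options said to reach 90% power is narrower than it appears.

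The attack-free proportion is one of the listed summaries of the primary endpoint. The 12-per-arm rows correspond to the 24-subject interim under 1:1 allocation, where the sponsor decides whether to continue Part 1. Someone relying on the table could read a non-significant attack-free comparison as stronger evidence against an effect than it is.

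**Working it through.** **Inputs.** Sample sizes, attack-free proportions and stated powers come from Protocol Table 6 (SAP Table 3). Two-sided alpha of 0.05 comes from the table note, Protocol 13.2.4 and SAP 12.1.1. Fisher's exact test comes from Protocol 13.2.4 and SAP 12.1.1.

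**Method.** For arms of size n0 (placebo) and n1 (active) with true proportions p0 and p1, exact power is the sum over all outcomes (x0, x1) of

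Bin(x0; n0, p0) × Bin(x1; n1, p1) × I[test rejects at (x0, x1)].

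Two rejection rules were compared:
- uncorrected Pearson chi-square: |x1/n1 − x0/n0| / √[p̄(1 − p̄)(1/n0 + 1/n1)] > 1.96, with p̄ = (x0 + x1)/(n0 + n1);
- two-sided Fisher: p ≤ 0.05.

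**Why the two differ.** Take 3/12 versus 8/12. Then p̄ = 11/24 and z = (5/12)/√[(11/24)(13/24)(2/12)] = 0.4167/0.2034 = 2.05, so chi-square rejects. The hypergeometric tail for three or fewer is 0.0436 + 0.0058 + 0.0003 = 0.0498 to four decimals, including a negligible last term. With equal arms the other tail is the same, so the two-sided Fisher p is 0.0995 and Fisher does not reject.

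**Step 1: reproduce the table.** Chi-square power, truncated to a whole percent, equals the stated value in 24 of 24 cells. Examples, with the stated value second:
- 12 per arm, 70% on active, placebo 15/20/25%: 85.28, 76.81, 67.02 against 85, 76, 67.
- 18 per arm, 70% on active, placebo 20/25/30%: 90.94, 83.51, 73.66 against 90, 83, 73.

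**Step 2: power of the planned test.** Each entry is stated → two-sided Fisher, in percent.

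| n per arm | Placebo | Active 70% | 75% | 80% | 85% |
|---|---|---|---|---|---|
| 12 | 15% | 85 → 72.2 | 91 → 81.4 | 95 → 88.9 | 98 → 94.3 |
| 12 | 20% | 76 → 61.0 | 84 → 71.6 | 91 → 81.2 | 95 → 88.9 |
| 12 | 25% | 67 → 49.7 | 76 → 60.8 | 84 → 71.6 | 91 → 81.4 |
| 18 | 20% | 90 → 83.5 | 95 → 90.9 | 98 → 95.8 | 99 → 98.4 |
| 18 | 25% | 83 → 73.1 | 90 → 83.3 | 95 → 90.9 | 98 → 95.9 |
| 18 | 30% | 73 → 60.9 | 83 → 73.1 | 90 → 83.5 | 95 → 91.3 |

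The smallest gap is 99 − 98.4 = 0.6 points. The largest is 67 − 49.7 = 17.3 points; at 18 per arm it is 73 − 60.9 = 12.1 points.

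**Step 3: count cells at 90% or more.** Stated: 6 at n = 12 and 9 at n = 18, total 15. Under Fisher: 1 and 6, total 7. So 5 of 6 are lost at n = 12 and 3 of 9 at n = 18, which is 8 of 15.

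**Step 4: pooled placebo.** With 18 active subjects, Fisher power was computed for three placebo totals:
- 20, the count in Protocol 5.3.3 ("20 subjects with HAE had received placebo");
- 22, the plan for Parts 1 to 3 (18 + 2 + 2);
- 24, with Part 4 added.

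| Placebo n | 20% vs 70% (stated 90) | 25% vs 75% (stated 90) | 30% vs 80% (stated 90) | 30% vs 70% (stated 73) | Largest shortfall against n = 18 rows |
|---|---|---|---|---|---|
| 20 | 87.8 | 87.0 | 87.1 | 66.3 | 6.7 |
| 22 | 86.3 | 85.6 | 86.9 | 63.6 | 9.4 |
| 24 | 88.9 | 88.1 | 88.8 | 67.3 | 5.7 |

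The three cells stated at exactly 90% stay below 90% in every case.

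**The case against.** **The chi-square attribution is an inference.** Neither document names a test. The match needs truncation; under ordinary rounding only 11 of 24 cells agree, and Table 5 appears to be rounded. A one-sided Fisher test at 0.05 gives the same powers to within about 0.01 point. This stands as a caution about the cause. The one-sided reading contradicts the table's own note, however, and on either reading the values are not the power of the planned two-sided test.

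**The largest gaps are in the least relevant rows.** Protocol 5.3.3 reports 18 subjects already treated at 350 mg and Part 3 under way, so the 24-subject decision is past, and the final analysis pools placebo. This is fair. With pooling, the shortfall is at most 5.7 to 9.4 points, and the three cells stated at 90% lose 1.1 to 4.4 points. A corrected table cannot change Part 1 enrolment.

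**No stated conclusion fails.** Protocol 13.1 selects no cell of Table 6. Its numeric assumptions concern the attack rate, which Table 5 covers, and Table 5 reproduces. Seven cells still reach 90%, so the claim to cover a range remains true, over a narrower range. Protocol 13.2.4 also says "There are no formal hypotheses planned for the study", and SAP 7.1 takes an estimation approach. These points limit the consequence. They do not make the printed powers right, because the plan still tests at 0.05 and offers the table in support of a 90% power statement.

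**Conclusion.** The concern holds. The stated powers exceed those of the planned two-sided Fisher's exact test in all 24 cells, by 0.6 to 17.3 points, and cells at 90% or more drop from 15 to 7. The result assumes independent binomial outcomes, the tabulated proportions and arm sizes, no dropout, and rejection at p ≤ 0.05. It does not depend on which test produced the table; an uncorrected chi-square is the only candidate tried that fits both the numbers and the two-sided note.

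This should be fixed, but it is a reporting error with limited reach. Type I error is unaffected, no planned analysis changes, and the attack-rate power stands.

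**What to change.** Keep Fisher's exact test; changing the analysis to suit the table would be the wrong remedy. In Protocol Table 6 and SAP Table 3, replace the 24 powers with the Fisher values in the Step 2 table, and state in the note that they are exact powers of a two-sided Fisher's exact test at 0.05. Rows for 18 active against 22 pooled placebo subjects would be a useful option, since they describe the planned final comparison for Parts 1 to 3.

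The cost is a less favourable table and one added phrase in each document, with no extra patients and no change to the planned analysis.

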## **13.2. Statistical Methods**

Subjects will be randomized in Part 1 in a 1:1 ratio to the 350mg BCX7353 QD and placebo QD treatment groups, in a 3:3:1 ratio to the 125 mg QD, 250 mg QD and placebo QD treatment groups in Part 2 in a 3:3:3:1 ratio to the 62.5 mg QD, 125 mg QD, 250 mg QD and placebo QD treatment groups in Part 3. Part 4, if conducted and if excluding a 62.5 mg dose, will have subjects randomized in a 1:6 ratio to the placebo QD and 175 mg QD treatment groups. Part 4, if conducted and if including a 62.5 mg dose, will have subjects randomized in a 1:6:3 ratio to the placebo QD, 175 mg QD, and 62.5 mg QD treatment groups. , Subjects randomized to the same treatment will be pooled across all study parts and Treatment Group 4 (62.5mg QD) will be pooled with Part 3 and 4, if conducted, for the final analyses of efficacy, safety, PD and PK/PD where applicable.

A detailed statistical analysis plan (SAP) will be developed and finalized prior to database lock at the conclusion of the study. The SAP will describe the methods of analyses/summaries, including all endpoints, time points, populations, missing data, etc. Any deviation from the analyses outlined in the SAP will be described in the final clinical study report.

### **13.2.1. Interim Analyses**

There will be one planned administrative interim in Part 1 of the study, after 24 subjects complete through the Day 28 dose. Sponsor employees not interacting with the site will receive unblinded primary and secondary efficacy tables and statistical output, at a minimum. Ad hoc analyses to enable discernment of treatment differences between the study drugs may be requested. At the conclusion of the interim analysis, a decision will be made to either continue enrollment into Part 1 or to close Part 1 and initiate Part 2 (dose ranging). A continuation of Part 1 may include up to 12 additional subjects for a total of up to 36 subjects completing Part 1 of the study. Additional administrative interim analyses will be conducted after completion of Parts 2 and 3 to support decision making for future development of the drug.

### **13.2.2. Analysis Populations**

The analysis populations are defined below.

#### **13.2.2.1. Full Analysis Set**

The FAS population will include all subjects who are randomized, receive at least 1 dose of study drug, and have post baseline HAE diary data recorded. Subjects will be analyzed according to the randomized treatment. The FAS population will be the population for efficacy analyses.

#### **13.2.2.2. Safety Population**

The safety population will include all subjects who received at least 1 capsule of study drug. Subjects will be analyzed according to the treatment received. This population will be used for all analyses of accountability, demographics, BCX7353 drug concentrations, and safety.

#### **13.2.2.3. Pharmacokinetic Population**

The PK population will include all subjects for whom PK parameters can be estimated. The PK population will be the primary population for the PK analysis.

#### **13.2.2.4. Pharmacodynamic Populations**

##### **13.2.2.4.1. Plasma Kallikrein Inhibition**

The PD population for plasma kallikrein inhibition will include all subjects for whom at least 1 pre- and postdose plasma kallikrein inhibition result can be estimated. This population will be used for all analyses of plasma kallikrein inhibition and for correlation with PK or BCX7353 concentrations.

##### **13.2.2.4.2. C1 INH**

There will be 1 additional PD population, for C1 INH functional levels. This PD population will include all subjects with a baseline and at least 1 postdose value and will be the primary population for the relevant PD analyses.

#### **13.2.3. Subject Demographic and Disposition Data**

Demographic data and baseline characteristics including age, gender, race or ethnicity, height at screening, weight at screening and BMI at screening will be summarized by treatment group using descriptive statistics.

Subject disposition will be presented for all subjects. The number of subjects who completed the study and discontinued from the study will be provided. The reasons for early discontinuation also will be presented. A tabulation of the number of subjects exposed to study drug and duration of exposure will be presented for each treatment group. Treatment adherence, dose modifications and reason for dose modifications will be provided as summaries.

#### **13.2.4. Analysis of Efficacy Variables**

As discussed in Section 7.2.1, each subject-reported HAE attack must be confirmed by an independent adjudication panel prior to inclusion in any statistical analysis or summary of efficacy.

There are no formal hypotheses planned for the study. The primary efficacy endpoint is the number of confirmed HAE attacks in the FAS population. The number of HAE attacks will be analyzed by treatment group using appropriate descriptive statistics as follows: weekly attack rate, counts of attacks, proportion of subjects with no attacks, and number of attack-free days. The relative change in attack rate from placebo will also be calculated for each active arm. Efficacy analyses will be conducted for HAE attacks reported over the entire dosing interval (Days 1 to 28 inclusive) and during the dosing period in which BCX7353 should be at steady-state conditions (Days 8 to 28, inclusive).

Efficacy endpoints will be summarized and listed for each treatment group. Between-treatment comparisons (active vs placebo and between active dose groups) for continuous efficacy variables will be performed using an analysis of variance (ANOVA) and an analysis of covariance (ANCOVA) model. The between treatment comparisons for the proportion of subjects who are attack free will be compared using a Fisher's exact test. A general linear model will be used to test the dose response. Additional statistical models may be considered and details will be provided in the statistical analysis plan.

There will be no adjustments for multiplicity and all statistical tests will be 2-sided with an alpha of 0.05.

Secondary efficacy endpoints including attack severity, location, duration and symptoms of attacks, and number of attacks requiring attack medication will be summarized for each treatment group.

### **13.2.5. Analysis of Safety Variables**

Adverse events will be mapped to a Medical Dictionary for Regulatory Activities (MedDRA) preferred term and system organ classification. Any event reported on the subject's study record that occurs on or after the initiation of study drug within a given treatment period is defined as treatment emergent. Additionally, it is assumed that an AE that is reported to have started on Day 1 without an associated onset time may have occurred after the initiation of study drug. Hence, AEs occurring on Day 1 with no associated onset time will be assumed to be treatment emergent. The occurrence of treatment-emergent AEs will be summarized by treatment group using MedDRA preferred terms, system organ classifications, and severity. Separate summaries of treatment-emergent SAEs and AEs considered to be related to study drug will be generated. All AEs will be listed for individual subjects showing both verbatim and preferred terms.

Descriptive summaries of vital signs, weight, ECG parameters, and clinical laboratory results will be presented separately for each study visit and treatment group. Laboratory abnormalities will be graded according to the DMID Adult Toxicity Table (Publish Date: Draft, November 2007, see Appendix 16.1).

Any graded abnormality that occurs following the initiation of study drug and represents at least 1-grade increase from the baseline assessment is defined as treatment emergent. The number and percentage of subjects experiencing treatment-emergent graded toxicities will be summarized by treatment group. Laboratory toxicity shifts from baseline to post baseline assessments will be summarized by study visit and treatment group. DLCO results will be presented as change from baseline in mL/min.

Clinically significant abnormal morphological ECG findings will be summarized by study visit.

Physical examination results will be presented in listings.

Concomitant medications will be coded using the World Health Organization (WHO) dictionary. These data will be summarized by treatment group.

